### Power analysis

Thirteen/fifteen (~87%) freezers had at least one freezing episode during the SIP task (mean number of freezes = 4.9, STD=+/- 2.47). Previous studies found an average of 66% improvement in freezing metrics between ineffective and effective stimulation conditions. A power analysis (paired t-test) using the mean number of freezes with ineffective/NO DBS (4.9, STD +/- 2.47, from above) and a 65% improvement from effective stimulation shows that the largest sample size required for significant outcomes is 9 subjects with freezing during SIP (alpha=0.05, power=0.8, assuming only 87% of patients will freeze during tasks).

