1. PURPOSE OF THE STUDY

a. Brief Summary

Continuous deep brain stimulation (cDBS) is an established therapy for the major motor signs in Parkinson's disease. Currently, cDBS is limited to "open-loop" stimulation, without real-time adjustment to the patient's state of activity, fluctuations and types of motor symptoms, medication dosages, or neural markers of the disease. The purpose of this study is to determine if an adaptive DBS system, responding to patient specific, clinically relevant neural or kinematic feedback, is more effective than continuous DBS on the motor Unified Parkinson's Disease Rating Scale (UPDRS III) and specific phenotypic measures in Parkinson's Disease.

b. Objectives

- 1). Determine the efficiency and effectiveness on PD signs of adaptive DBS (aDBS), triggered by patient-specific resting state neural activity, compared to continuous DBS (cDBS) using the UPDRS III and validated, high-resolution kinematic metrics of tremor, bradykinesia and freezing of gait (FOG).
- 2). Determine whether aDBS using a kinematic classifier pertinent to the patient specific phenotype is more efficient and/or effective on PD symptoms than aDBS using the using the patient's specific resting state neural classifier and/or cDBS.
- 3). Determine whether aDBS is more efficient and effective than cDBS in the optimized on medication state after six months of cDBS. We believe that the results of these experiments will make it possible for DBS to realize its full potential: a new generation of context-dependent, continuously adaptive DBS devices will have the ability to sense and modulate brain signals that are correlated to abnormal movement and will provide DBS therapy in different locations based on motor phenotype and state of activity.

c. Rationale for Research in Humans

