## Statistical Analysis Plan

### Data Analysis

Concurrent Kinematic and Neural Recording: The kinematic signals from the wireless Opal sensors and tri-axial accelerometer are sampled at 128 Hz and 1 kHz, respectively. Video recordings (thirty frames/second) are acquired concurrently with the LFP signals (sampled at 1 kHz) using our data acquisition interface and Spike software. The data from the wireless Opal sensors is collected using Mobility Lab software (APDM, Inc., Portland, OR).

Neural Signal Analysis: Signal analysis will be performed in MATLAB (version 8.2, The MathWorks, Inc., Natick, MA, USA). Prior to analysis, the data will be parsed into rest, movement, and various stimulation state epochs using Spike software, with care being taken to exclude any sections containing signal or movement artifacts from further analysis. Spectrograms of LFP epochs will be generated using a short-time Fourier transform of a one second Hann filtered sliding window and 50% overlap. The power spectral density (PSD) estimate will be calculated using Welch's method with the aforementioned windows and overlap parameters. Phase-amplitude coupling (PAC) between pairs of frequency (i.e. phase and amplitude components) will be calculated using Tort's modulation index (MI). Signals will be band-pass filtered using a two-way least square FIR filter with 1 Hz frequency resolution for phase and 2 Hz frequency resolution for amplitude; frequencies will be used to account for correcting the frequency leakage in higher frequencies. A surrogate data analysis will be performed to assess the statistical significance of MI values extracted for each frequency pair and MI values will be converted to z-scores. A PAC map will be formed to show PAC values (z-scores) between each frequency pair (phase and amplitude) for each subject.

Kinematic Analysis: During the FW and TBC tasks, the wireless Opal sensors will be used to measure gait speed, stride and swing duration, gait arrhythmicity and asymmetry, and the number and duration of freezing episodes, as detailed in Section During the SIP task, we will evaluate the stepping cycle rhythmicity and symmetry and the number and duration of freezing episodes on force plates.

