### Comparison of characteristics at baseline

Student's t-tests were used to compare age, disease duration, pre-op and post-op Unified Parkinson's disease Rating Scale (UPDRS) between the Freezer and Non-Freezer groups.

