### **Analysis of primary outcome**

The number and percentage of occurrences of treatment-related adverse events (AE) will be reported for each treatment arm of continuous DBS (cDBS), adaptive DBS (aDBS) and off DBS.

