### **Analysis of secondary outcomes**

For Alpha/beta power and Sample Entropy (SampEn): Alpha/beta power varied across subjects sometimes by orders of magnitudes. Relative alpha and beta power was calculated by dividing the summed absolute alpha or beta power by the summed power in the 40- 70 Hz band during the resting state, and allowed comparison across subjects, whose raw signal magnitude can vary by one or two orders of magnitude, see Supplementary information. The FW task was analyzed by excluding the turning periods at the end of the 10 m of straight walking. As a result, each FW task had 4 trials.

Similarly, as the TBC task had four trials, it was also analyzed as four separate time periods for each patient. The SIP task had one trial per patient. Asymmetry and arrhythmicity were assessed individually using a linear mixed effect model in Freezers and Non-Freezers during FW, while a one-way ANOVA was used in SIP. A one way ANOVA and a Kruskal-Wallis test by ranks was also used to determine if alpha or beta power and SampEn changed significantly between Freezers and Non-Freezers in SIP, while a linear mixed effects model was used for both TBC and FW, in order to account for the four trials. Freezer or Non-Freezer type was a fixed effect and a factor variable with 2 levels (Freezer and Non-Freezer). Subject STN was a random effect, and a random intercept was used in the model. Residuals were assessed for homoscedasticity and normality, and all statistical assumptions were met.

To compare arrhythmicity, asymmetry, or stride time between groups, a one-way ANOVA was used. Paired t-tests were used to compare the effects of different stimulation frequencies on arrhythmicity, asymmetry, and stride time within each group for each task. Post hoc analyses were completed to compare between stimulation conditions. All statistical testing was performed in SigmaPlot (Systat Software, San Jose, CA) using two-tailed tests with significance levels of  $P < .05$ .

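### The SAP's only power calculation is for a paired t-test of SIP freeze counts that its analysis sections do not list, and no efficacy test is given for aDBS versus cDBS, the protocol's stated question

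*SAP*

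**What the plan says.** **The question.** Protocol section 1a asks whether an adaptive system "is more effective than continuous DBS on the motor Unified" Parkinson's scale (UPDRS III) and on phenotype-specific measures. Objective 1 in section 1b has neural-triggered aDBS "compared to continuous DBS (cDBS) using the UPDRS III and validated, high-resolution kinematic metrics of tremor, bradykinesia and freezing of gait (FOG"). Objective 2 adds aDBS with a kinematic classifier. Objective 3 takes aDBS versus cDBS into the optimized on-medication state after six months of cDBS. Section 2a (Specific Aims 1b and 2b) times the outcomes at 30 minutes of aDBS or cDBS. The endpoint entry in section 2g is NA.

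**The power calculation.** SAP, Power analysis: "A power analysis (paired t-test) using the mean number of freezes with ineffective/NO DBS" (mean 4.9, SD 2.47), a 65% improvement with effective stimulation, alpha 0.05, power 0.8, and an allowance for only 87% freezing. The result is 9 subjects.

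**The analyses.**
- Data Analysis says that the SIP task will yield "the number and duration of freezing episodes on force plates".
- The baseline section compares "Rating Scale (UPDRS) between the Freezer and Non-Freezer groups".
- The primary outcome is treatment-related adverse events, as numbers and percentages "for each treatment arm of continuous DBS (cDBS), adaptive DBS (aDBS) and off DBS".
- The secondary section compares Freezers with Non-Freezers on alpha/beta power, sample entropy, asymmetry, arrhythmicity and stride time. It then says "Paired t-tests were used to compare the effects of different stimulation frequencies on arrhythmicity, asymmetry, and stride time within each group for each task", followed by "Post hoc analyses were completed to compare between stimulation conditions".

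**The concern.** A power calculation should describe a test that the plan goes on to carry out, and the plan should test the question the study was set up to answer. Here neither link is made. The freeze count is measured and powered but then drops out. The aDBS-versus-cDBS contrast, which runs through all three objectives, reaches the SAP only as a layout for adverse event counts.

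Two things are at stake. A reader may take the stated 80% power as applying to the study's main contrast, which it does not. And because the SAP names no aDBS-versus-cDBS test and no main comparison, several remain open when results are written up: neural or kinematic aDBS, initial programming or six months, UPDRS III or one of the kinematic metrics.

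**Working it through.** **1. Reproduce the plan's figure.** Inputs from SAP, Power analysis: mean 4.9, SD 2.47, 65% improvement, alpha 0.05, power 0.80, 87% freezing. Two-sided testing is taken from the last sentence of Analysis of secondary outcomes. The SD of the paired difference is not given; it is assumed to be 2.47.

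- Difference: 0.65 × 4.9 = 3.185 freezes.
- Standardized difference: d = 3.185 / 2.47 = 1.289.
- Paired t-test power from the noncentral t with n − 1 degrees of freedom and noncentrality d√n: 0.715 at n = 6 and 0.810 at n = 7, so 7 are needed.
- Allowance for non-freezing: 7 / 0.87 = 8.05, rounded up to 9.

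The stated 9 is reproduced under that assumption.

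**2. Look for the powered test among the analyses.**

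| SAP section | What is analysed | Contrast | Freeze counts tested? |
|---|---|---|---|
| Power analysis | Number of SIP freezes | Ineffective/no DBS vs effective stimulation | Powered |
| Comparison of characteristics at baseline | Age, disease duration, UPDRS | Freezers vs Non-Freezers | No |
| Analysis of primary outcome | Adverse events, descriptive | cDBS, aDBS, off DBS | No |
| Analysis of secondary outcomes, group tests | Alpha/beta power, sample entropy, asymmetry, arrhythmicity, stride time | Freezers vs Non-Freezers | No |
| Analysis of secondary outcomes, paired t-tests | Arrhythmicity, asymmetry, stride time | Stimulation frequencies | No |
| Analysis of secondary outcomes, post hoc sentence | Not named | Stimulation conditions, not specified | Not named |

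The paired t-tests that are listed differ from the powered one in both outcome and contrast.

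**3. Look for the protocol's question in the same table.** Only the adverse event row names aDBS and cDBS, and it is descriptive. Only the baseline row uses UPDRS, and there the contrast is between patient groups. The tremor and bradykinesia measures of objective 1 are in no row.

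**4. What a paired aDBS-versus-cDBS comparison could detect.** The documents give no expected difference or SD for this contrast, so only standardized figures are possible. The number with both measurements is also uncertain:

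- Protocol section 8a allows up to 34 subjects; section 9d ends the study at 30.
- Up to 15 subjects are also enrolled in the earlier protocol (section 8a). Section 2a says that such subjects join at follow-up or at an extra session, and that they may complete the aims.
- If all 15 lacked a measurement at initial programming (an assumed extreme), 30 − 15 = 15 or 34 − 15 = 19 would remain.

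Solving the step 1 power formula for d at 80% power, two-sided 0.05:

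| Subjects with both measurements | Detectable difference (SDs of the paired difference) |
|---|---|
| 15 | 0.78 |
| 19 | 0.68 |
| 30 | 0.53 |
| 34 | 0.50 |

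**The case against.** The strongest reply is that much of what seems absent can be found elsewhere. The Power analysis section gives the freeze-count test, its outcome, its contrast and its alpha, and the secondary section makes all testing two-tailed at .05. For aDBS versus cDBS, the protocol supplies UPDRS III, the 30-minute measurement and the six-month on-medication repeat. This stands, and it limits the point. A reader might infer that the comparison has no named measure or time point at all, and the protocol does not support that. What is missing is a test in the SAP and a choice of main comparison. Likewise the freeze-count test is stated once, as a basis for sample size, and is not carried into the analyses.

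A second reply is that the primary outcome is a descriptive safety tabulation and needs no power calculation. That is right. But the SAP goes on to plan inferential tests and a power calculation, and these match neither each other nor objectives 1 to 3.

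A third is that the post hoc sentence covers the contrast. It could, but it names no outcome, no pair of conditions and no test, so it fixes nothing in advance.

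Two further inferences should be resisted. One is that 9 is wrong: it reproduces in the working. The other is a false-positive rate obtained by carrying the secondary section's paired tests over to aDBS versus cDBS. Nothing in the SAP says they will be used that way.

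**Conclusion.** The point holds as a mismatch between plan and question. The SAP's stated 80% power belongs to a paired t-test of SIP freeze counts that its analysis sections do not list. Followed as written, the SAP would not test whether aDBS is more effective than cDBS on UPDRS III. This rests on the text of the power, baseline, primary and secondary sections, all of which are present without redaction marks.

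No effect on power in clinical units can be given for aDBS versus cDBS, because the documents contain no SD for it. In standardized terms the detectable difference runs from 0.78 to 0.50 SD as the number with both measurements goes from 15 to 34. The lower end assumes that every subject from the earlier protocol lacks the initial-programming measurement. The correction is cheap and should be made.

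**What to change.** **In Analysis of secondary outcomes, add:**

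(a) A paired t-test of the number of SIP freezes in freezers, off DBS versus the condition that the sponsor means by effective stimulation, two-sided 0.05, identified as the comparison in the power analysis.

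(b) A paired comparison of UPDRS III after 30 minutes of neural-triggered aDBS (objective 1) versus 30 minutes of cDBS, in all subjects with both measurements at their first such session, named as the main efficacy comparison. Kinematic aDBS, the six-month on-medication repeat (objective 3) and the freezing, tremor and bradykinesia metrics would be reported as paired differences with 95% confidence intervals.

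**In Power analysis, add** a sentence that the calculation does not cover aDBS versus cDBS. If a detectable difference is quoted, tie it to the number with both measurements, using the last table in the working, and not to total enrolment.

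**Cost.** Two analysis entries and one or two sentences on power. Planned visits, stimulation conditions and enrolment stay as they are. Protocol section 2a words some of the testing as optional, so the numbers with paired data should be reported. The real price is that one comparison must be named as main and the others become supportive. The sponsor may prefer another main comparison, but should name it before the data are analysed.

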### Comparison of characteristics at baseline

Student's t-tests were used to compare age, disease duration, pre-op and post-op Unified Parkinson's disease Rating Scale (UPDRS) between the Freezer and Non-Freezer groups.

### **Analysis of primary outcome**

The number and percentage of occurrences of treatment-related adverse events (AE) will be reported for each treatment arm of continuous DBS (cDBS), adaptive DBS (aDBS) and off DBS.

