The Nexus D and Nexus E systems are a newly developed technology allowing for bi-directional communication of information between the Activa® PC+S and a portable computer (PC). The PC will use real time neural and kinematic data to develop classifiers of the behavioral states of rest, tremor, and bradykinesia in PD. The investigator team will develop a series of algorithms (control policies) on the PC, which will inform the Activa® PC+S to turn ON or OFF (at a preset, safe and therapeutic setting) based on the kinematic or neural classifiers of PD. Using this established neural interface for the first time in human PD subjects, we will develop optimal patient-specific customized classifier and control policy algorithms. This will drive the future creation of closed-loop neuromodulation devices, embedding and automating sensing and stimulating platforms.

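### The protocol asks whether adaptive DBS beats continuous DBS, but the SAP specifies no aDBS-versus-cDBS estimate or test on any efficacy or efficiency outcome

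*SAP*

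**What the plan says.** **Protocol.** Section 1a sets the purpose as finding out whether aDBS "is more effective than continuous DBS on the motor" UPDRS, together with phenotypic measures. In section 1b:

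- Objective 1 compares neurally triggered aDBS with cDBS "using the UPDRS III and validated, high-resolution kinematic metrics of tremor, bradykinesia and freezing of gait (FOG").
- Objective 2 is to "Determine whether aDBS using a kinematic classifier pertinent to the patient specific phenotype is more efficient and/or effective on PD symptoms" than neural aDBS and/or cDBS.
- Objective 3 is to "Determine whether aDBS is more efficient and effective than cDBS in the optimized on medication state after six months of cDBS".

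Section 2a (SA1b and SA2b) has outcomes measured once a 30-minute run of either mode is complete, and repeats Aims 1 and 2 on medication at six months. Section 2g, Study Endpoint(s), reads NA.

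**SAP.** Under Analysis of primary outcome: "The number and percentage of occurrences of treatment-related adverse events (AE) will be reported for each treatment arm", the arms being cDBS, aDBS and off DBS. No contrast or test is given. UPDRS appears only under Comparison of characteristics at baseline, between Freezers and Non-Freezers. The secondary analyses test Freezer status or stimulation frequency.

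**The concern.** A SAP should carry the trial's main question through to a named outcome, contrast and method. Here the analyses it does specify, followed exactly, answer a different question. Any aDBS-minus-cDBS result produced later would be chosen after the fact from several outcomes, two classifier types, two medication states and several visits.

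Two further points follow.

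- The protocol does not say that every subject receives both modes, or in what order. A later comparison may therefore mix mode with period, fatigue, practice or carry-over. The documents do not allow the size of this to be judged.
- The adverse-event table cannot stand in for the missing comparison. Protocol section 9a limits Nexus-E to study visits, whereas Objective 3 refers to six months of cDBS, and the SAP gives no observation window. If events during chronic cDBS are counted, the percentages are not comparable between modes.

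**Working it through.** **1. Protocol outcomes set against the SAP**

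| Protocol outcome | What the SAP does with it | aDBS vs cDBS specified? |
|---|---|---|
| UPDRS III | Baseline t-test on UPDRS, Freezers vs Non-Freezers | No |
| Tremor | Not mentioned | No |
| Bradykinesia | Not mentioned | No |
| Freezing number and duration | Measured (Kinematic Analysis); no test named under secondary outcomes | No |
| Efficiency (all 3 objectives) | Not mentioned; not defined in the protocol either | No |

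The SAP does analyse asymmetry and arrhythmicity, which the protocol links to freezing. It does so by Freezer status (mixed model or one-way ANOVA) or by stimulation frequency (paired t-tests). The mixed model's only named fixed effect is Freezer type. One sentence mentions post hoc comparison of stimulation conditions, without naming the conditions, the outcome or the method.

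**2. Does the protocol fill the gap?** No. Endpoints are NA. Recording UPDRS III after each run is a fair reading of sections 1 and 2a, but it is not explicitly scheduled: section 2a makes tasks other than rest and wrist movement optional during closed-loop stimulation.

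**3. Does the SAP's sample size cover the question?** Inputs from Power analysis: mean 4.9 freezes with ineffective or no DBS, SD 2.47, 65% improvement, alpha 0.05, power 0.80, 87% of patients freezing. Two-sided testing is stated under secondary outcomes.

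- Difference used: 0.65 × 4.9 = 3.185 freezes.
- SD of paired differences, equal SDs and correlation r: 2.47 × √(2(1 − r)). At r = 0.5 this is 2.47.
- Standardised difference: 3.185 / 2.47 = 1.29.
- Paired t-test (noncentral t): 7 pairs, power 0.81.
- Inflation: 7 / 0.87 = 8.05, rounded up to **9**, the SAP's figure.

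The SAP does not state r = 0.5. Other correlations give:

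| r | SD of difference | Pairs | ÷ 0.87, rounded up |
|---|---|---|---|
| 0 | 3.49 | 12 | 14 |
| 0.3 | 2.92 | 9 | 11 |
| 0.5 | 2.47 | 7 | 9 |
| 0.7 | 1.91 | 6 | 7 |

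In every row the contrast is effective against ineffective or no stimulation.

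**4. Room left for aDBS over cDBS.** Assume cDBS itself gives the 65% reduction.

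- Mean freezes remaining on cDBS: 0.35 × 4.9 = 1.715.
- Largest further reduction as a share of the difference used: 1.715 / 3.185 = 0.54.

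The documents give no SD for freezes on stimulation, and no SD or target difference for UPDRS III. No required sample size or power for aDBS versus cDBS can be computed.

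**The case against.** The strongest defence is that this is an early study of a new interface, for which a descriptive safety primary is reasonable. That is fair: the adverse-event count is not wrong in itself. The defect is its mismatch with a protocol whose stated purpose is comparative effectiveness, and restating that purpose is a legitimate way to resolve it.

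A second defence is the post hoc sentence, which may be meant to include aDBS and cDBS. It follows tests of stimulation frequency on three gait metrics and specifies nothing, so it cannot serve as the planned test of the main question.

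Third, the SAP refers to a section whose number is missing and to supplementary information, so detail may exist elsewhere. The statement here is therefore limited to the supplied text. The primary and secondary analysis sections are nevertheless present, and neither contains the contrast.

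Three smaller points stand:

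- The 54% is illustrative. The SAP does not say that effective stimulation means cDBS, and the figure bounds improvement in freezes only.
- Needing no extra patients holds for an estimate with an interval, not for a claim of adequate power.
- A period effect cannot be fitted to completed runs whose order was not recorded.

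**Conclusion.** The concern holds and must be fixed. None of Objective 1's four outcome domains has a specified aDBS-versus-cDBS estimate or test, and efficiency, named in all three objectives, has no measure. The SAP's sample size of 9 reproduces only under an unstated correlation of 0.5 and belongs to a different contrast. If cDBS achieves the assumed 65%, the most that aDBS could add is 1.7 freezes against the 3.2 used. The main conclusion rests on reading the two documents together and does not depend on that arithmetic. The points on run order and adverse-event exposure are conditional, because the documents state neither the order nor the observation window.

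**What to change.** **1. Reconcile the two documents, by one of two routes.**

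*Route A: keep the effectiveness purpose.* Add to the SAP:

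- A within-subject aDBS-minus-cDBS analysis of UPDRS III with a 95% CI. Use a paired analysis, or a mixed model with condition, visit/medication state and (where order is known) period as fixed effects and subject as random effect. Lead contrast: neural aDBS versus cDBS, off medication.
- Tremor, bradykinesia and freezing by the same contrasts, as supportive outcomes, with a signed-rank test or count model for freeze numbers.
- Kinematic aDBS versus cDBS and versus neural aDBS (Objective 2), with the neural and kinematic contrasts repeated at the six-month on-medication visit (Objective 3).
- Kinematic results by phenotype. Only bradykinesia aDBS is described with a wrist task every 2 minutes, so state whether its cDBS comparator run carries the same task load.
- For subjects from the earlier protocol, which visit supplies the lead contrast, and results with and without them.
- One efficiency measure. Share of each run with stimulation on is a natural candidate, since the algorithms tell the device "to turn ON or OFF (at a preset, safe and therapeutic setting) based on the kinematic or neural classifiers of PD". Otherwise remove efficiency from the objectives.

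State in the protocol that each subject receives both modes and that UPDRS III is recorded after each run; where it was not, use the outcomes that were. Parts of the SAP are in the past tense, so disclose that this analysis was specified afterwards for any data already analysed.

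*Route B: safety and feasibility.* Revise the protocol purpose and state that efficacy is exploratory, with no superiority conclusion.

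**2.** Randomise the order of 30-minute runs not yet done, and record order for all runs where it can be established.

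**3.** Report adverse events in laboratory runs by condition, separately from events during chronic cDBS.

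**Cost.** A rewritten SAP section and one or two protocol sentences. No extra patients for an estimate with a CI; precision is unknown. Some added assessment time per run if UPDRS III is not already taken.
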